#### **5.4.1.2 The average daily duration of sunlight exposure without prodromal symptoms**

The following is the procedure to calculate the duration of sunlight exposure without prodromal symptoms. The analysis windows are defined in the table 4.

1. Step 1 in section 5.4.1.1 will be applied.
2. The duration of sunlight exposure without prodromal symptoms in a day is calculated. It is the sum of the duration of sunlight exposure periods deducting the prodromal symptom presenting time covered in each period.
3. Step 3 to 5 in Section 5.4.1.1 will be applied.

The following endpoint is derived when applying the rule above without the step 1.

5.4.1.2.1 The average daily duration of sunlight exposure regardless of time of day without prodromal symptoms

#### **5.4.1.3 The average daily mean duration of sunlight exposure without prodromal symptoms**

The following is the procedure to calculate the average daily mean duration of sunlight exposure without prodromal symptoms. The analysis windows are defined in the table 4

1. Step 1 in section 5.4.1.1 will be applied.
2. The duration of sunlight exposure without prodromal symptoms in a day is calculated. It is the sum of the duration of sunlight exposure periods deducting the prodromal symptom presenting time covered in each period. This sum of duration is divided by the number of sunlight exposure periods as the average daily mean duration.
3. Step 3 to 5 in Section 5.4.1.1 will be applied.

#### 5.4.2 Definition of baseline

Unless otherwise specified, the baseline values are the last available assessment before the first dose of randomized treatment.

#### 5.4.3 Definition of (percent) change from baseline

For numerical variables, change from baseline will be calculated as the post-baseline value minus the baseline value. If percent change from baseline is required, then percent change from baseline will be calculated as the change from baseline divided by the baseline value, multiplied by 100. If baseline value cannot be determined for a particular variable, the change from baseline and percent change from baseline will not be calculated.

#### 5.4.4 Analysis visits for the non-diary data

The analysis visits will be derived for the non-diary data. The analysis windows are different from the windows used for diary data.

Unless stated otherwise, the analysis visit windows for by visit summary in efficacy and safety endpoints are defined in the table below.

**Table 5 Analysis Visit Windows for the non-diary data**

Analysis visit	Nominal day	Window
Screening	Day -14	By Day -14
Day 1	First dose day	NA
Week 1	Day 8	Day 3 to 11
Week 2	Day 15	Day 12 to 22
Week 4	Day 29	Day 23 to 42
Week 8	Day 57	Day 43 to 71
Week 12	Day 85	Day 72 to 99
Week 16	Day 113	Day 100 to 134
Week 22 (FU)	Day 155	NA
End of treatment (EOT)	Week 16 study visit or study early termination visit	

The analysis visits are derived according to the following criteria:

- The unscheduled visits are not used for the deriving.
- If a study visit is the only one in an analysis visit window, this study visit becomes the derived analysis visit.
- If there are multiple visits in an analysis visit window, the closest visit to the nominal day becomes the analysis visit. In the event that two visits are the closest visits to the nominal day and equally distanced to the nominal day, the visit after the nominal day becomes the derived visit.
- The follow-up visit will not be derived. The study visit will be used.

- Unscheduled visits and retests (same visit number assigned), will not be displayed in by-visit summary tables, but will be included in the data listings.
- The deriving analysis visit is not applicable to the data not depending on study visit, for example, the AE data.

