5.3.2.2 Visit 3 (Week 1, Day 8±5)

Subjects will undergo mobile laboratory sample collection and blood samples will be taken and the following assessments will be performed by the central laboratory (please refer to Table 5.1-1 for details regarding the complete time and events schedule for this study):

- Liver function marker evaluations (ALT, AST, GGT, ALP, direct and total bilirubin).

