5.3.2.3 Visit 4 (Week 2, Day 15±5)

Subjects will undergo mobile laboratory sample collection and blood samples will be taken and the following assessments will be performed by the central laboratory (please refer to Table 5.1-1 for details regarding the complete time and events schedule for this study):

- Liver function marker evaluations (ALT, AST, GGT, ALP, direct and total bilirubin).

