5.3.2.4 Visit 5 (Week 4, Day 29±7)

The following assessments will be performed (please refer to Table 5.1-1 for details regarding the complete time and events schedule for this study):

- Abbreviated physical examination (including body weight).
- Vital signs (including sitting blood pressure, pulse rate, and oral body temperature).
- Routine laboratory evaluations (hematology; biochemistry; coagulation; urinalysis).
- Urine pregnancy test (for female subjects of child-bearing potential only).
- Blood sampling for PK analysis.
- Dispensing of MT-7117 or placebo.
- Medication accountability.
- Review sunlight exposure diary (re-educate subject if necessary).
- AE and concomitant medication recording.

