10.2.3 Safety Assessments

Adverse Events

AEs are considered as treatment-emergent if they occur after the first dose administration of study drug or if a pre-dose event increases in severity following dosing.

AEs will be assumed to be treatment-emergent, unless there is clear evidence (if necessary through comparison of partial dates) to suggest that the AE started prior to the first dose of IMP.

The frequency and incidence of treatment-emergent AEs (TEAEs) will be summarized by system organ class (SOC) and preferred term (PT) by treatment period and overall. Summaries will also be produced by relationship to study drug and by maximum severity. The summary will be sorted by International Agreed Order for SOC and alphabetical order for preferred term (or by frequency from the highest to the lowest).

The following summaries will be presented:

- Summary of TEAEs by SOC and PT.
- Summary of TEAEs by SOC, PT and severity.
- Summary of TEAEs by SOC, PT and relationship.
- Summary of Serious TEAE by SOC and PT.
- Summary of TEAE leading to drug withdrawn by SOC, PT.

For each of the summaries produced at the subject level, multiple occurrences of the same event within a subject will be counted once in the summaries by SOC and preferred term; multiple occurrences of the same event within a subject will be counted once in the maximum severity category (severe > moderate > mild) and/or maximum study drug

relationship category (reasonable possibility/no reasonable possibility). If severity or relationship is found to be missing, the most severe occurrence will be imputed for that particular summary.

Safety laboratory tests

Routine laboratory safety tests include hematology, coagulation, biochemistry and urinalysis.

Continuous laboratory parameters will be summarised by scheduled time point and treatment group. Observed values as well as changes from baseline (Day -1) will be summarized by treatment groups. Categorical parameters will be summarized by frequency counts and percentages of subjects within each category.

The laboratory data will be listed in full with clinically relevant values flagged (L=Lower than normal range, H=Higher than normal range or A=Abnormal if no reference range).

The number of subjects with post baseline assessments \geq x3 ULN and \geq x5 ULN and so on will be calculated for ALT, AST, GGT, ALP, direct and total bilirubin and summarized by treatment for each post baseline visit.

Vital signs and electrocardiogram data

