### 1.2 Study Design

This is a Phase II, randomized, double-blind, placebo-controlled study to assess the efficacy, tolerability, and safety of MT-7117 in subjects with EPP. The study consists of a 2-week screening period, a 16-week double-blind treatment period, and a 6-week follow-up period at Week 22. The total participation period is approximately 24 weeks.

This study is being conducted without regard to seasonality.

The study design is illustrated in Figure 1.

Subjects will attend Screening (Visit 1) up to 2 weeks before Randomization (Visit 2), in order to confirm eligibility and obtain pre-study safety assessments including nevi evaluation. Subjects will also be instructed how to use a sunlight exposure diary.

At Visit 2, subjects meeting eligibility criteria will be randomized in a 1:1:1 ratio to receive either [redacted], [redacted] of MT-7117, or matching placebo in a double-blind manner. Baseline average daily sunlight exposure time without prodromal symptom ( $\leq 30$  min and  $>30$  min) will be used as stratum for the randomization. The first dose will be administered at Visit 2 following baseline assessment including in-clinic sunlight exposure test. Active or placebo tablets will be administered once daily in the morning with food.

Subjects will attend in-clinic visits at Weeks 4, 8, and 12 (Visits 5, 6, and 7, respectively) during which assessments will be performed. In addition, subjects undergo mobile laboratory sample collection at Weeks 1 and 2 (Visits 3 and 4, respectively) to measure liver function markers (AST, ALT, GGT, ALP, direct and total bilirubin).

Subjects will attend the end of treatment visit at Week 16 or early termination (Visit 8). Following the last treatment visit, subjects will attend a follow-up visit at Week 22 or 6 weeks after early termination.

[figure not shown]

Figure 1 Study Design Schematic

Table 1 Schedule of Assessments

Study Period	Screening		Double-blind Treatment									Follow-up
	Visit 1	Week -2	Visit 2 (Randomization)	Visit 3 f Week 1	Visit 4 f Week 2	Visit 5 Week 4	Visit 6 Week 8	Visit 7 Week 12	Visit 8 n (EOT) Week 16	Visit 9 o (EOS) Week 22		
Study Week	~Day -14 a		Day 1	Day 8±5	Day 15±5	Day 29±7	Day 57±7	Day 85±7	Day 113±7	Day 155±10		
Informed consent b,c	X											
Inclusion/exclusion criteria evaluation	X		X									
Demographics	X											
Medical history	X		X									
Randomization			X									

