### 7.12.2 Laboratory Tests

Lab test values and changes from baseline will be summarized descriptively by treatment and visit.

The lab tables will be generated for each Lab categories (Hematology, Coagulation, Biochemistry and Urinalysis).

All laboratory data will be listed with clinically relevant values flagged (L=Lower than lower limit of normal range, H=Higher than upper limit of normal range or A=Abnormal).

The number and percentage of subjects with lab values out of normal range for each lab test will be summarized in table by treatment. The percentage will be based on the number of subjects of safety population in the corresponding group.

In addition, following clinical relevant ranges (and flags) will also be considered for summary table. The count and percent of subjects meeting the criteria will be presented. The percentage will be based on the number of subjects of safety population in the corresponding group.

- ALT and/or AST  $\geq 3 \times$  Upper Limit of Normal Range (ULN), 4xULN, 6xULN, 10xULN
- AST and/or ALT  $\geq 3 \times$  ULN with Total bilirubin  $\geq 2 \times$  ULN
- Total bilirubin  $\geq 2 \times$  ULN

- Creatinine  $\geq 2 \times$  ULN
- ALP  $\geq 3 \times$  ULN
- Hy's Law (ALT or AST  $> 3 \times$  ULN and TBL  $> 2 \times$  ULN and Alkaline phosphatase  $< 2 \times$  ULN)

The figure of mean (or median) and standard error value of ALT, AST, Total bilirubin and Alkaline phosphatase by visit will be plotted.

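### SAP Table 5 files a compliant Week 4 visit on Day 22 under Week 2, which leaves Week 4 empty for that subject in the by-visit safety summaries

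*SAP*

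**What the plan says.** Protocol 5.3.2.2 to 5.3.2.4 give the visit windows as "Visit 3 (Week 1, Day 8±5", "Visit 4 (Week 2, Day 15±5" and "Visit 5 (Week 4, Day 29±7". Visits 3 and 4 collect liver markers only. Visit 5 adds the full laboratory panel, vital signs and an abbreviated physical examination.

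SAP 5.4.4 and Table 5 set the analysis windows for by-visit summaries of non-diary efficacy and safety data, unless stated otherwise: Week 1 is Days 3 to 11 (nominal Day 8), Week 2 is Days 12 to 22 (nominal Day 15) and Week 4 is Days 23 to 42 (nominal Day 29). A visit that is alone in a window takes that window's label. For more than one, "If there are multiple visits in an analysis visit window, the closest visit to the nominal day becomes the analysis visit", with the later visit winning a tie. Unscheduled visits are not used. Only follow-up is exempt: "The follow-up visit will not be derived. The study visit will be used".

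These labels feed SAP 7.12.2, where "Lab test values and changes from baseline will be summarized descriptively by treatment and visit", the by-visit plots of ALT, AST, total bilirubin and alkaline phosphatase in the same section, and the vital-sign and physical-examination tables in SAP 7.12.3 and 7.12.5. Protocol 10.2.3 also describes counts of liver-marker elevations "summarized by treatment for each post baseline visit".

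**The concern.** The Week 2 window runs two days past the last compliant Visit 4 (Day 20) and takes in the first compliant Visit 5 (Day 22). A subject who attends Visit 5 on that day has followed the protocol, yet the Week 4 result is either shown as Week 2 or left out of the summary. Nothing in the SAP exempts compliant scheduled visits.

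At stake is the completeness and labelling of the early by-visit safety tables. The liver-marker tables matter most, because protocol 3.2 gives frequent liver monitoring as a deliberate feature of the design. With 34 subjects planned per arm, one or two missing Week 4 values would be visible.

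**Working it through.** **1. Reproduce Table 5.** The cut-points are midpoints of adjacent nominal days:

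- (8+15)/2 = 11.5, so Week 1 ends at Day 11.
- (15+29)/2 = 22, given to the earlier week.
- (29+57)/2 = 43, given to the later week.
- (57+85)/2 = 71, (85+113)/2 = 99 and (113+155)/2 = 134, all given to the earlier week.

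All match. Day 22 is a tie day: 22−15 = 7 and 29−22 = 7. Table 5 already gives one tie day, Day 43, to the later week.

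**2. Compare with the protocol windows.**

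| Visit | Compliant days | Table 5 window for that week | Compliant days given another label |
|---|---|---|---|
| 3 (Week 1) | 3–13 | 3–11 | 12, 13 → Week 2 |
| 4 (Week 2) | 10–20 | 12–22 | 10, 11 → Week 1 |
| 5 (Week 4) | 22–36 | 23–42 | 22 → Week 2 |

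Visits 6, 7 and 8 (Days 50–64, 78–92 and 106–120) have no mismatch.

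**3. Follow a Visit 5 on Day 22.** It lies 7 days from Day 15. A Visit 4 on Days 12–20 lies at most 5 days from Day 15, so Visit 4 always wins and Visit 5 is dropped. If Visit 4 was on Days 10–11, it is labelled Week 1 and Visit 5 fills Week 2. In both cases Week 4 has no scheduled visit. Examples, as days of Visits 3/4/5:

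- 8/15/22: Visit 5 is dropped and Week 4 is empty.
- 3/10/22: Visit 4 is shown as Week 1, Visit 5 is shown as Week 2, Visit 3 is dropped and Week 4 is empty.

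**4. Count the allowed combinations.** With Visit 3 before Visit 4, there are 11×11−10 = 111 day pairs, times 15 days for Visit 5, giving 1,665 triples. Visit 5 is on Day 22 in 111 of them, and Week 4 is empty in all 111. Visit 5 is dropped in 111−15 = 96; in the other 15, Visit 4 is on Days 10–11.

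**5. The Visit 3/4 overlap.** Visit 3 on Days 12–13 gives 15 pairs × 15 = 225 triples. Visit 4 on Days 10–11 also gives 225. The two sets cannot coincide, and each shares 15 triples with Day 22. The total losing at least one value is 225+225+111−15−15 = 531 of 1,665 (31.9%).

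**6. Move the tie day.** With Week 2 at Days 12–21 and Week 4 at Days 22–42, the empty Week 4 cases fall from 111 to 0. The total falls from 531 to 450 (27.0%), all of it from the Visit 3/4 overlap on Days 10–13.

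**7. Range for the share of subjects.** Actual visit timing is not in the documents, so every figure here is an assumption.

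- Day 22 alone: 0% if Visit 5 stays within ±6 days. With weights rising evenly from 1 at each end of the window to 8 at Day 29 (sum 64), it is 1/64 = 1.6%. With days equally likely, it is 1/15 = 6.7%, or 34/15 ≈ 2.3 subjects per arm.
- All three mismatches, days equally likely within the stated spread (Visits 3 and 4 / Visit 5): 0 of 637 for ±3/±6; 49 of 735 (6.7%) for ±3/±7; 274 of 1,170 (23.4%) for ±4/±7; 531 of 1,665 (31.9%) for the full windows.

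**The case against.** Midpoint windows are an ordinary convention, and labelling by actual day is what analysis windows are for. A Day 12 sample is 3 days from Day 15 and 4 from Day 8, so calling it Week 2 describes its timing better than its visit number does. The follow-up exemption is also a weak precedent: follow-up comes six weeks after the end of treatment, so in early terminators it has no fixed study day.

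This stands for Visits 3 and 4. A reader might infer that Table 5 mishandles those visits through a poor choice of cut-points. The documents do not support that: the protocol windows themselves overlap on Days 10–13, so no set of non-overlapping day windows could separate them, and visit label against actual day is a debatable choice. Nor is a value always lost. If the competing visit was missed, the remaining value is only relabelled.

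The defence does not cover Day 22. It is equally far from both nominal days, so closeness gives no reason to call it Week 2, and no compliant Visit 4 can fall on it. The only compliant scheduled visit on that day is Visit 5.

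**Conclusion.** The point holds as a minor, avoidable cut-point error. A compliant Visit 5 on Day 22 is labelled Week 2, is dropped when Visit 4 was attended on Days 12–20, and leaves Week 4 empty. This assumes that no other usable visit, such as an early-termination visit, falls on Days 23–42. It also takes the rule at its word, as choosing between whole visits, so that all laboratory and vital-sign results from Visit 5 go together. If it is applied test by test, only the liver markers compete with Visit 4, and the other Visit 5 results are shown as Week 2.

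Three stronger readings are tempting and not supported:

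- That about a third of subjects would lose data. The 32% counts allowed day combinations as if visits were spread evenly; it is not a forecast.
- That safety detection or the main result is at risk. Listings keep every value. The subject-level threshold counts in SAP 7.12.2 are not described as by visit. The AESI and withdrawal rules do not use Table 5, and the primary endpoint uses the diary windows in Table 4. Any by-visit elevation counts produced under protocol 10.2.3 would carry the mislabelling if they used Table 5.
- That screening data are lost because the Screening row stops at Day −14, although "Subjects will attend Screening (Visit 1) up to 2 weeks before Randomization (Visit 2". That row reads as loose wording, and baseline is defined separately in SAP 5.4.2.

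**What to change.** In Table 5, before unblinding, set Week 2 to Days 12–21 and Week 4 to Days 22–42. This removes all Week 4 gaps for compliant visits and changes the label of no other compliant visit. The one side effect concerns a visit already out of window: a late Visit 4 on Day 22 would be labelled Week 4. The cost is one edited boundary and the matching line in the visit derivation, with no change to data collection. SAP 7.1 lets it be adopted as a data handling rule at the blinded data review.

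Optionally, let compliant scheduled visits keep their study visit label and use the day windows only for early-termination or out-of-window visits, with out-of-window defined by the protocol limits so that no discretion enters. This also clears the Visit 3/4 collisions. The price is slightly looser timing: a Day 13 sample could be reported as Week 1 and a Day 10 sample as Week 2. In either case, state whether the closest-visit rule applies to whole visits or test by test.

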5.3.2.6 Visit 7 (Week 12, Day 85±7)

The following assessments will be performed (please refer to Table 5.1-1 for details regarding the complete time and events schedule for this study):

- Abbreviated physical examination (including body weight).
- Vital signs (including sitting blood pressure, pulse rate, and oral body temperature).
- Routine laboratory evaluations (hematology; biochemistry; coagulation; urinalysis).
- Urine pregnancy test (for female subjects of child-bearing potential only).
- Blood sampling for PK analysis.
- Dispensing of MT-7117 or placebo.
- Medication accountability.
- Review sunlight exposure diary (re-educate subject if necessary).
- AE and concomitant medication recording.

5.3.2.7 Visit 8: End of Treatment Visit (Week 16, Day 113±7 or Early Termination)

Subjects will attend the end of treatment visit at Week 16 or early termination. The following assessments will be performed (please refer to Table 5.1-1 for details regarding the complete time and events schedule for this study):

- Abbreviated physical examination (including body weight).
- 12-lead ECG.
- Vital signs (including sitting blood pressure, pulse rate, and oral body temperature).
- Routine laboratory evaluations (hematology; biochemistry; coagulation; urinalysis).
- Plasma porphyrin and erythrocyte protoporphyrin sample collection.
- Urine pregnancy test (for female subjects of child-bearing potential only).

- Blood sampling for PK analysis (at the visit and 3 to 4 hours after the first PK sample collection [both post-dose]).
- Medication accountability.
- Subject Questionnaire for study medication.
- PROMIS-57 questionnaire.
- PGIC.
- Review sunlight exposure diary (re-educate subject if necessary).
- Melanin density evaluation as measured by spectrophotometer.
- Nevi evaluation and biopsy (for any nevi of clinical concern to the dermatologist or other qualified site staff).
- Optional skin biopsy for exploratory pharmacodynamics analysis.
- In-clinic sunlight exposure test: Perform a formalized collection of the subject's time to onset of 1st prodromal symptom in sun-exposed setting (e.g. preferably outside or by window) using timer.
- AE and concomitant medication recording.
- Fitzpatrick skin type assessment.

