5.3.3 Follow-up (Visit 9, Week 22, Day 155±10)

Subjects will return to the study site for a follow-up visit at 6 weeks after end of treatment visit (Week 16 or early termination). The following assessments will be performed (please refer to Table 5.1-1 for details regarding the complete time and events schedule for this study):

- Abbreviated physical examination (including body weight).
- Vital signs (including sitting blood pressure, pulse rate, and oral body temperature).
- Routine laboratory evaluations (hematology; biochemistry; coagulation; urinalysis).
- Urine pregnancy test (for female subjects of child-bearing potential only).
- PROMIS-57 questionnaire.
- PGIC and PGIC_2.
- Review sunlight exposure diary.
- Melanin density evaluation as measured by spectrophotometer.
- Nevi evaluation (and biopsy for any nevi of clinical concern based on the opinion of the dermatologist or other qualified site staff).
- AE and concomitant medication recording.
- Exit interview questionnaire (The exit interview questionnaire can be assessed at Visit 9 or as a post study follow-up phone call or online survey.)

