  - The figure of LS mean with standard error will be plotted.
- Change from baseline in average daily mean intensity of the patient's pain events during 16 week double-blind treatment period.
  - The model will include fixed categorical terms for treatment, randomization strata, visit, and treatment by visit interaction together with continuous covariate terms for baseline value and baseline value by visit interaction.
  - The figure of LS mean with standard error will be plotted.
- Change from baseline for all total score and total score in each domain of Physical Function, Anxiety, Depression, Fatigue, Sleep Disturbance, Ability to Participate in Social Roles and Activities, Pain Interference, Pain intensity in PROMIS-57.
  - The model will include fixed categorical terms for treatment, randomization strata, visit, and treatment by visit interaction together with continuous covariate terms for baseline value and baseline value by visit interaction.
  - The figure of LS mean with standard error will be plotted by all total score and total score in each domain of PROMIS-57.
- PGIC
  - The model will include fixed categorical terms for treatment, randomization strata, visit, and treatment by visit interaction.
  - The figure of LS mean with standard error will be plotted.

The following secondary endpoint will be listed and summarized by treatment and planned time point using descriptive statistics. The value of melanin density, change from baseline and % change from baseline in melanin density at Week 8, 16, and 22 by skin segments and average of 6 skin segments will be plotted by treatment. For average of 6 skin segments for the value of melanin density, change from Baseline and % change from baseline in melanin density at Week 8, 16, and 22, will be analyzed using MMRM similar to the analyses for the primary endpoint.

- The change from baseline and % change from baseline in melanin density at Week 8, 16, and 22 by skin segments.
- Average of 6 skin segments for the change from Baseline and % change from baseline in melanin density at Week 8, 16, and 22.

The value of melanin density, change from baseline and % change from baseline in melanin density at Week 8, 16, and 22 by skin segments and average of 6 skin segments will be plotted by treatment.

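### SAP Table 5 can leave an early leaver's end-of-treatment melanin value out of the melanin model, yet enters that subject's off-drug follow-up as Week 22 whatever its day

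*SAP*

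**What the plan says.** **Schedule.** The protocol visit lists place melanin density at Visit 2 (5.3.2.1), Visit 6 (5.3.2.5), Visit 8 (5.3.2.7) and Visit 9 (5.3.3). The lists for Visit 5 (Week 4) and Visit 7 (Week 12) do not contain it.

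**Early leavers.** Protocol 5.3.2.7 states: "Subjects will attend the end of treatment visit at Week 16 or early termination". An early leaver therefore has the Visit 8 assessments on leaving. Protocol 5.3.3 then asks for a "follow-up visit at 6 weeks after end of treatment visit (Week 16 or early termination").

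**Windows.** SAP Table 5 assigns non-diary visits by study day: Week 1 is Days 3–11, Week 2 Days 12–22, Week 4 Days 23–42, Week 8 Days 43–71, Week 12 Days 72–99 and Week 16 Days 100–134. If two visits share a window, the one closer to the nominal day is kept. Visit 9 has no window: "The follow-up visit will not be derived. The study visit will be used". A separate EOT row takes the "Week 16 study visit or study early termination visit".

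**Model.** SAP 7.11.2 says that for the six-segment average, "change from Baseline and % change from baseline in melanin density at Week 8, 16, and 22, will be analyzed using MMRM". The EOT row is named for no efficacy analysis in 7.11.2; its stated use is ECG (7.12.4). The plots of the primary endpoint against melanin in SAP 7.11.3 pool the same three weeks.

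**The concern.** Two rules act on the same subject. Visit 8 is placed by day and Visit 9 by label. For some early leavers the value taken at the end of treatment gets a week that the melanin model does not contain, while the value taken six weeks after stopping enters as Week 22.

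Three things are at stake. The Week 22 term mixes subjects who had 16 weeks of drug with subjects who may have had only a few. Through the within-subject covariance, that off-drug value also informs the subject's missing Week 16 value, as if it had followed a full course. Finally, the pooled plots lose the end-of-treatment pair and keep the follow-up pair. Melanin density is a secondary endpoint, and Protocol 3.2 justifies the follow-up period by pigmentation recovery.

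**Working it through.** The plan states no figure to reproduce here. The inputs are the Table 5 windows, the protocol visit lists and the six-week (42-day) follow-up interval.

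**1. How the windows were built.** The edges follow the midpoints of adjacent nominal days: (8+15)/2 = 11.5, (15+29)/2 = 22, (29+57)/2 = 43, (57+85)/2 = 71, (85+113)/2 = 99 and (113+155)/2 = 134. Weeks 1, 2, 4 and 12 are there because other assessments are scheduled then.

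**2. Where an early-termination Visit 8 goes.**

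| Termination day | Table 5 label | In melanin model? |
|---|---|---|
| 3–42 | Week 1, 2 or 4 | No |
| 43–71 | Week 8 | Yes, unless a closer Visit 6 exists |
| 72–99 | Week 12 | No |
| 100–134 | Week 16 | Yes |

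Days 3–42 are 40 days and Days 72–99 are 28, so 40 + 28 = 68 of the 97 days from Day 3 to Day 99 (70%). In addition, a termination on Days 58–71 loses to a Visit 6 held on Day 57 under the closest-visit rule.

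**3. Sensitivity to leaving times.** The documents give none, so these are assumptions.
- Uniform over Days 2–105: 68/104 = 65%. Uniform over Days 2–112: 68/111 = 61%.
- Early-weighted leaving (exponential, mean 28 or 56 days): 71–81%.
- Late-weighted leaving (weight rising with day or day squared): 49–71%.

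**4. Where Visit 9 falls.** Day of Visit 9 = termination day + 42; its label is always Week 22 (nominal Day 155).

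| Termination | Visit 9 | Days before Day 155 | Table 5 window containing that day |
|---|---|---|---|
| Day 29 | Day 71 | 84 | Week 8 |
| Day 57 | Day 99 | 56 | Week 12 |
| Day 80 | Day 122 | 33 | Week 16 |
| Day 85 | Day 127 | 28 | Week 16 |

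The protocol range for Visit 9 starts at 155 − 10 = Day 145, and 145 − 42 = 103. Any termination before Day 103 therefore puts Visit 9, held at exactly six weeks, outside that range.

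**5. What melanin-specific windows would recover.** The same midpoint rule on the melanin schedule gives (1+57)/2 = 29 and (57+113)/2 = 85, so Week 8 is Days 29–85 and Week 16 is Days 86–134. Of the 68 days:
- Days 29–42 and 86–99 are recovered: 14 + 14 = 28 days (41%).
- Days 3–28 (26 days) still have no modelled week.
- Days 72–85 (14 days) lose to Visit 6 where it was held. The Day 80 case is one of these.

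The largest distances from a nominal day are 57 − 29 = 28 and 85 − 57 = 28 for Week 8; for early values in Week 16, 113 − 86 = 27.

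**The case against.** **Grouping follow-up by time off drug is defensible.** Protocol 3.2 describes the follow-up as six weeks after the end of treatment or early termination, and everyone at Visit 9 is about six weeks past the end-of-treatment visit. This stands in part. It supports showing these values, and a sensitivity analysis that includes them. It does not support calling Day 71 Week 22 in a model whose other terms are defined by study week.

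**The model does not keep only off-drug data for every early leaver.** A reader might infer that it does. Leavers on Days 72–99 normally have an on-drug Week 8 value from Visit 6. Only terminations on Days 3–42 (40 of 97 days, 41%) would typically leave off-drug data alone. The early-termination values are also not lost from the data, because the EOT row retains them; no efficacy model uses that row.

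**New windows bring their own mixing.** A Day 86 value would enter the Week 16 term and a Day 29 value the Week 8 term. This is true and is a cost. It follows the midpoint rule that Table 5 already uses.

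**PROMIS-57 and PGIC are less certain.** By the protocol visit lists, their post-baseline measurements are also only at Visits 6, 8 and 9. Their models contain visit without naming the weeks ("The model will include fixed categorical terms for treatment, randomization strata, visit, and treatment by visit interaction"), so a Week 4 or Week 12 level could hold only a few early leavers. In the available text of SAP Table 1, however, the columns are displaced and marks for these two appear in other positions. If Weeks 4 and 12 were scheduled for them, only Days 3–22 (20 of 97, 21%) would be unscheduled. Melanin is the firm case.

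**Few subjects may be involved.** Protocol 4.5 encourages those who stop treatment to complete all visits, so the point concerns only those with an actual early-termination visit. This stands.

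**Conclusion.** The point holds for melanin density. As written, the plan leaves out of the model end-of-treatment values from early terminations on Days 3–42 and 72–99, and enters follow-up values as Week 22 even when they fall well before the protocol's own range for that visit. The exclusion of unscheduled visits in SAP 5.4.4 does not remove the problem, because an early-termination visit is Visit 8.

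A reader might infer from 70% that most early leavers are affected. The documents do not support that. The figure counts calendar days, not subjects; other assumed leaving patterns give about 49–81%, and the share would be small if leavers clustered on Days 43–71 or after Day 99. Nor can the shift in the Week 22 mean be derived, since the documents give no dropout rate, no attendance at Visit 9 after early termination and no rate of pigment loss.

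The diary-based primary endpoint uses Table 4 and is unaffected. This is a worthwhile correction to a secondary analysis, not a threat to the trial's main result.

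**What to change.** In SAP 5.4.4:

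1. Give assessments scheduled only at Weeks 8 and 16 their own windows: Week 8, Days 29–85; Week 16, Days 86–134. Apply this to melanin, and to PROMIS-57 and PGIC once their schedule is confirmed against the protocol visit lists.
2. Summarise under EOT the early-termination values that still do not enter the model: Days 3–28, and Days 72–85 where Visit 6 was held.
3. Label Visit 9 after early termination as *6 weeks after early termination*. Keep it out of the Week 22 term of the melanin MMRM and out of the Week 22 data in the pooled plots, and report it separately by length of treatment.
4. Add a sensitivity analysis that includes these Visit 9 values in the Week 22 term, because all subjects are then about six weeks past their end-of-treatment visit.

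Item 3 is the essential change: it removes the mislabelled follow-up value in every such case, whereas item 1 is only a partial remedy.

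The cost is a few lines of text and some programming, with no new data. The downside is a few fewer Week 22 observations, and some early-termination values up to 28 days from the nominal day in the Week 8 or Week 16 term.
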